### 6.2 Eligibility

Each subject will be evaluated by the Investigator to assess his suitability for entry into this study according to the following criteria:

#### 6.2.1 Inclusion Criteria

- Subject will be older than 18 years of age
- Subject was diagnosed with enlarged prostate of  $\geq 30$  gr volume
- Subject is a candidate for surgery treatment
- Subject is willing and has signed the Informed Consent Form
- AUA score  $\geq 12$
- Qmax  $< 15$  mL/s

Any of the following will exclude the subject from the study:

#### 6.2.2 Exclusion Criteria

- Need to perform concomitant procedure, other than prostate vaporization
- PVR  $> 300$ mL
- Current Urine retention and Pdet  $< 40$  cm H2O

**Description: Surgical. Protocol LUM-SBU-VP-15-02, Ablation efficacy of contact side firing fiber in predefined settings for treating BPH**

- Documented or suspected prostate cancer and / or bladder cancer
- Neurogenic bladder disorder / neurogenic voiding dysfunction
- Urethral strictures
- Previous prostatic, bladder neck, or urethral surgery
- Known history of spinal cord injury
- Urogenital trauma
- Bladder neck stricture
- Evidence of urinary tract infection
- History of chronic prostatitis

## 7 Study Procedures

### 7.1 Study duration and timelines

For each subject the duration of the study will be of 3 months. Subjects may remain hospitalized following surgery, based on physician's discretion. Subjects will be followed at the day of their discharge from the hospital. Each subject will return for follow-up visits at 1 and 3 months following the treatment procedure at which time they will have completed their participation in the study.

It is expected that enrollment of all study subjects at the site will occur within 12-16 weeks from study initiation.

### 7.2 Study Measures

7.2.1.1 Various assessments will be performed throughout the study at different time-points as detailed in fiber positioning, vaporization control and ability to successfully complete the procedure.

Table 1.

#### 7.2.2 Objective Measures

7.2.2.1 Blood workup: including CBC, BMP, & PSA

7.2.2.2 Urine workup: including urine analysis, and urine culture if applicable

7.2.2.3 BPH volume will be performed using trans-rectal ultrasound prior to the procedure.

All imaging verifying the diagnosis, pre-intervention images, intra-operative (during laser activation) images, immediate post-operative and follow-up images will be recorded on electronic media for documentation, further analysis and data recording.

Subject anonymity will be assured for all images by deleting any ID detail. Only the code for the Case Number in the study will appear on the records being transferred to the sponsor.

7.2.2.4 BPH treatment will be confirmed and three months post discharge using trans rectal ultrasound.

#### 7.2.2.5 Investigator Subjective Assessments

**Description: Surgical. Protocol LUM-SBU-VP-15-02, Ablation efficacy of contact side firing fiber in predefined settings for treating BPH**

Revision: B  
 State: Released  
 ECO No: GEN-0007426  
 Effective Date: 02-Jun-2016

7.2.2.6 Procedure Questionnaire will record subjective usability parameters including visibility impairment and resolution (due to bleeding or other disturbances), fiber positioning, vaporization control and ability to successfully complete the procedure.

Table 1 – Assessments time-points:

Assessment	Baseline (Pre- operative)	Performed During Visit			
		Perioperative	Hospital discharge	1 month follow- up	3 month follow- up
Subject assessment (ICF, medical history, demographics, inclusion/exclusion evaluation)	X				
Trans Rectal Ultrasound	X				X
Post Void Residual Ultrasound	X			X	X
Q-Max Uroflow	X			X	X
Urodynamic Evaluation	X				
Blood analysis (CBC, BMP & PSA) & urine analysis	X	X (CBC)			X
Urine culture (if applicable)	X				X
Erectile Dysfunction	X				X
Subject Questionnaires (AUA, QoL)	X			X	X
Physician Subjective Procedure Questionnaire		X			
Adverse Event Assessment		X	X	X	X

## 7.3 Screening Procedures

### 7.3.1 Subject Enrollment

**Description: Surgical. Protocol LUM-SBU-VP-15-02, Ablation efficacy of contact side firing fiber in predefined settings for treating BPH**

1. During the first visit, the investigator will screen the subject for eligibility to participate in the clinical study using the Inclusion & Exclusion criteria. During screening, the study physician will review the subject's medical history to ensure that the subject meets the study criteria.
2. If the subject has met the preliminary study eligibility criteria, the study physician will obtain an informed consent from the subject, clearly indicating his/her understanding of the procedure, requirements and risks involved with study participation and other applicable treatment options. It will be understood that no compensation will be payed to the subjects for participating in the clinical study.
3. The subject will be enrolled to the study and the treatment will be scheduled.

### **7.3.2 Subject Identification**

At enrollment, each subject will receive an identifying number that will include a consecutive serial number. The subject identification number and the subject initials will be used to identify the subject during the entire study and will be entered in the subject's CRF for each treatment.

### **7.4 Pre-treatment evaluation**

The following examinations are included in the standard of practice for subjects with PBH and may have been performed prior to the subject enrollment. Medical history as well as measurements that were completed prior to study enrollment will be used as baseline data for the study.

A complete history and physical examination and total duration of the patient's symptoms:

Blood and urine tests including urinalysis, urine cultures, complete blood count (CBC), BMP & PSA, BPH volume and other analysis measured using the most recent trans rectal ultrasound performed.

### **7.5 BPH treatment pre-operative preparations (according to hospital routine of care)**

#### **7.5.1 Anesthesia**

The subject will be put under regional (spinal) anesthesia or general anesthesia, per standard hospital practice for BPH procedures.

#### **7.5.2 Preoperative antibiotics**

The subject will be given intravenous preoperative antibiotics per standard hospital practice.

### **7.6 Procedure**

#### **7.6.1 Cystoscopy and Fiber introduction**

The subject will be placed in dorsal lithotomy position. A 21 F cystoscope will be inserted through the urethra and the entire lower tract will be inspected to assess the degree of obstruction and to rule out presence of urethral stricture, bladder neck contracture or unexpected bladder pathology (tumors, stones).

**Description: Surgical. Protocol LUM-SBU-VP-15-02, Ablation efficacy of contact side firing fiber in predefined settings for treating BPH**

The Xpeeda laser fiber will be introduced through the cystoscope and vaporization of the prostate is initiated (settings: frequency-60Hz, energy 2J, power-120W).

### **7.6.2 Vaporization**

Initially, a bladder neck groove is performed at the 5 o'clock and 7 o'clock positions with direct light contact with the tissue. If a significant median lobe is present, this will be vaporized between the 2 grooves.

Following this, the lateral lobes of the prostate will be vaporized from 1 o'clock to 5 o'clock, and from 11 o'clock to 7 o'clock positions. Next, the roof tissues will be vaporized from the level of the bladder neck to the level of the veru montanum if necessary. Lastly, apical tissues will be vaporized with care to avoid ablation of the veru montanum and external sphincter. Coagulation will be utilized as necessary (settings: frequency-20Hz, power-20W)

At the end of the procedure, the entire lower tract will be inspected to assure an open channel and rule out any significant bleeding. A 22F catheter will be inserted – traction and continuous bladder irrigation can be utilized as necessary

## **7.7 Follow - up Regimen**

Each subject will be evaluated by the physician post the procedure as per standard of care to assess subject wellness. Subjects will be released from the hospital per the hospital standard practice. Each subject will return one month and 3 months following the procedure for a follow-up visits to assess prostate condition and subject well-being. Evaluations during each of these visits will be performed as described in Table 1. Additional unscheduled visits or examinations performed that are not part of the standard of care will be recorded in a dedicated Case Report Form (CRF).

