## 3 Study Design

This is a one arms, prospective, single center study. Subjects will undergo a single treatment for ablation of the prostate using the study device. Follow up visits are scheduled for the day of release

**Description: Surgical. Protocol LUM-SBU-VP-15-02, Ablation efficacy of contact side firing fiber in predefined settings for treating BPH**

from the hospital and at 1 and 3 months post procedure. Additional treatment sessions, if required, will be at the discretion of the investigator, as part of the site standard of practice. Additional sessions will not be included in this study.

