##### 5.1.2.2 2. Perioperative complications

- Urinary Retention
- Haematuria
- Dysuria
- Infection
- Urge incontinence
- Stress incontinence
- Erectile Dysfunction (International Score as compared to baseline)

**Description: Surgical. Protocol LUM-SBU-VP-15-02, Ablation efficacy of contact side firing fiber in predefined settings for treating BPH**

- Re-catheterization
- Readmission for secondary operation

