#### **9.1.3 Serious Adverse Events**

NOTE: The term serious is not synonymous with severity, which may be used to describe the intensity of an event experienced by the subject. An AE that does not meet any of the below criteria will be classified as non-serious.

A serious adverse event is any event that:

4. led to death,
5. led to serious deterioration in the health of the subject, that either resulted in:
  - 5.1. a life-threatening illness or injury, or
  - 5.2. a permanent impairment of a body structure or a body function, or
  - 5.3. in-patient or prolonged hospitalization, or
  - 5.4. medical or surgical intervention to prevent life-threatening illness or injury or permanent impairment to a body structure or a body function,
6. led to foetal distress, foetal death or a congenital abnormality or birth defect

Any adverse events or complications reported by the patient or observed by the physician that occur during or after treatment with the device will be recorded in the medical record or source document and on the dedicated Case Report Form. The investigator will determine if the AEs are device related or procedure related. This assessment shall include the onset date, resolution date, severity, seriousness, frequency, additional treatment required and outcome.

Each adverse event should be assessed according to the following criteria:

**Description: Surgical. Protocol LUM-SBU-VP-15-02, Ablation efficacy of contact side firing fiber in predefined settings for treating BPH**

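### A subject re-treated before 3 months stays in the analysis with both sessions' tissue credited to the first session, and a repeat procedure treated as standard practice may go unrecorded

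*Combined protocol and SAP*

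**What the plan says.** Three rules decide what happens to a subject who needs more treatment.

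- **Section 3 (Study Design):** "Additional treatment sessions, if required, will be at the discretion of the investigator, as part of the site standard of practice". The next sentence adds: "Additional sessions will not be included in this study".
- **Section 7.7 (Follow-up Regimen):** "Additional unscheduled visits or examinations performed that are not part of the standard of care will be recorded" on a dedicated CRF. Nothing comparable is said there about contacts that are standard of care.
- **Section 6.1 (Source and Sample Size):** the only stated ground for removal from the performance analysis is failure to return at 1 and/or 3 months.

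These bear on two sets of primary endpoints. Section 5.1.1 bases ablation rate and ablation efficacy on TRUS volume before treatment and at 3 months, divided by procedure time and by energy used. Section 5.1.2.2 lists "Re-catheterization" and "Readmission for secondary operation" among the perioperative complications, without a time window.

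A separate route exists for adverse events. Section 9.1.3 requires that any adverse event or complication during or after treatment "will be recorded in the medical record or source document and on the dedicated Case Report Form", with an assessment that covers "additional treatment required and outcome". Table 1 schedules adverse event assessment perioperatively, at discharge, and at 1 and 3 months.

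**The concern.** The efficacy measures are meant to describe what one session achieves per minute and per unit of energy. The numerator is fixed by a scan at 3 months, so it includes anything done to the gland in between. If a repeat session counts as outside the study, its time and energy do not reach the denominator, while the tissue it removed does reach the numerator. No rule sets such a subject aside or marks him. Qmax, PVR and AUA at 3 months would likewise describe two treatments and be reported as the result of one.

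On the safety side, the same two sections leave it unclear whether a repeat session or a catheterization regarded as ordinary care will be written down as an endpoint event. With 20 subjects, one event more or less is visible in the result.

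**Working it through.** The plan gives no re-treatment rate, expected complication rate or sample size derivation, so there is no figure of its own to reproduce. The check is a reading of the sections together, followed by illustrative arithmetic.

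**1. Path of a re-treated subject through the efficacy analysis**

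- Repeat session before 3 months: site standard practice and not included (Section 3).
- Dedicated CRF for unscheduled contacts: not required, because the contact is standard practice (Section 7.7).
- 3-month visit attended: not removed from the performance analysis (Section 6.1).
- 3-month TRUS enters ablation rate and ablation efficacy (Section 5.1.1). These are two of the three primary efficacy measures; ablation time is not affected.

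Nothing in Section 8.1 or 8.2 interrupts this path.

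**2. Size of the effect on ablation rate**

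Reading the Section 5.1.1 formula as volume reduction over time, let V be the volume removed in the first session, T its duration, and f the second session's volume as a fraction of V.

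- Intended rate: V/T. Rate as computed: (V + fV)/T = (1 + f) × V/T.
- Overstatement for that subject: f. The same holds for volume over energy.
- Overstatement of the mean of 20, with k re-treated subjects and all subjects otherwise alike: k × f/20.

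Assumed inputs, not in the documents: 20 mL in the first session and 5-10 mL in the second, so f = 5/20 to 10/20 = 0.25 to 0.50. The case f = 1 is an upper illustration.

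| k | f = 0.25 | f = 0.50 | f = 1 |
|---|---|---|---|
| 1 | 1.25% | 2.5% | 5% |
| 2 | 2.5% | 5% | 10% |
| 3 | 3.75% | 7.5% | 15% |

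**3. Chance that the case arises**

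The probability of at least one re-treated subject among 20 is 1 − (1 − p)^20. For assumed 3-month risks p of 2%, 5%, 10% and 15% it is 33%, 64%, 88% and 96%.

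**4. Which safety events have a recording route**

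- Section 5.1.2.2 lists both events as complications, and Section 9.1.3 sends complications to a CRF with no exception for standard of care. A catheter for retention, or a return to theatre for bleeding, should therefore be recorded.
- Section 9.1.4.3 says a pre-existing condition is not reported as an adverse event without a substantial increase in severity or frequency. Enlarged prostate is the pre-existing condition in every subject, so a second session for residual tissue could be placed under this exemption.
- The seriousness criterion "in-patient or prolonged hospitalization" sits under serious deterioration in health. An elective readmission need not meet it, so 24-hour reporting under Section 9.2.1 is likely but not assured.

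**5. Size of one missed event**

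1/20 = 5 percentage points. Exact (Clopper-Pearson) 95% intervals: 0/20 gives 0-16.8%; 1/20 gives 0.1-24.9%.

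**The case against.** The strongest reply concerns safety, and much of it stands. A reader might infer from Sections 3 and 7.7 that re-catheterization and re-operation are left out of data capture altogether. The documents do not support that. Section 7.7 governs one form, for unscheduled contacts. Safety data have their own route through Section 9.1.3, Section 5.1.2.2 names both events as complications, and adverse events are assessed at four scheduled points. Section 8.2 also commits to analysing all endpoints. The sentence in Section 3 can be read as saying only that a repeat session is not a study treatment, which does not contradict Section 5.1.2.2.

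A reader might also infer a systematic bias in the device's favour. A missed event can only lower a complication count, but that presumes the Section 9.1.3 route fails, and for most events it should not. Nor do the documents describe a staged second treatment; additional sessions arise only if required. The CRF list announced in Section 10.5 does not appear in the available text, so whether the forms already have fields for these events cannot be determined.

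Finally, the study is descriptive, with no threshold or comparator, and the shift in the mean is small. That is fair as to size.

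What the reply does not reach is the efficacy point: no text says how a re-treated subject's 3-month volume or functional data are handled. Nor does any sentence say that the two safety endpoints are collected whatever the standard-of-care status of the contact.

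**Conclusion.** The point holds in two parts of unequal strength.

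**Efficacy.** As the rules stand, a subject re-treated before 3 months is analysed with both sessions' tissue over the first session's time and energy, and his 3-month Qmax, PVR and AUA are contaminated too. The overstatement is 25-50% for that subject and about 1.3-2.5% in the mean of 20 per re-treated subject. This rests on assumed volumes, on reading the formula as volume reduction, and on Section 3 meaning that second-session time and energy are left out. The effect on functional endpoints cannot be sized from the documents.

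**Safety.** The gap is narrow: a repeat session or catheterization regarded as standard practice and not classed as an adverse event. Each one missed moves a rate by 5 percentage points.

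The change is worth making before data are collected. The main reason is that results would be attributed to the wrong treatment; the shift in the mean is modest.

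**What to change.** 1. Reword Section 7.7 so that every unscheduled visit, catheterization, readmission and repeat prostate procedure through 3 months is recorded on a CRF with its date, whether or not it is standard of care.
2. Reconcile Section 3 with Section 5.1.2.2: state that an additional session is not a study treatment but is counted as a safety endpoint event.
3. In Section 8.1, state that the 3-month volume-based endpoints and Qmax, PVR and AUA will be reported with and without subjects re-treated before that visit. Both are needed: keeping these subjects credits the first session with later work, while dropping them may remove those in whom the first session achieved least.

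This concerns recording and analysis only; it does not touch the decision to re-treat. The cost is a few more CRF entries at one site and one sensitivity analysis, with no added visits or procedures.

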# **8 Study Analysis Plan**

## **8.1 Study Analysis**

The results of the study: subject demographics, baseline assessments, treatment parameters, treatment evaluations and follow-up assessments will be summarized and descriptive analysis will be performed. Adverse events reported will be listed, documenting course, outcome, severity, and possible relationship to the treatment. The modified Clavien classification will be used to evaluate severity of Adverse Events [2].

## **8.2 Interim report**

Interim analysis of the immediate post-operative data will be performed after at least 10 subjects underwent surgery in order to assess the immediate study results. If applicable, most of the study endpoint analysis will be performed for the initial 10 patients including ablation duration, safety parameters and secondary end-points (if applicable according to follow-up scheduled). Treatment

**Description: Surgical. Protocol LUM-SBU-VP-15-02, Ablation efficacy of contact side firing fiber in predefined settings for treating BPH**

safety and adverse events report, durations and all endpoints will be analyzed following the completion of all study subjects follow-up period and summarized in the final report.

## **9 Adverse Events (AE)**

### **9.1 Adverse Events Definitions**

#### **9.1.1 Adverse Event**

Any untoward medical occurrence, unintended disease or injury, or untoward clinical signs (including abnormal laboratory findings) in subjects, users or other persons, whether or not related to the investigational medical device

#### **9.1.2 Adverse Device Effect**

Adverse event related to the use of an investigational medical device. Adverse Device Effect can be an anticipated serious adverse Device Effect which by its nature, incidence, severity or outcome has been identified in the risk analysis report or unanticipated if it has not been identified in the risk analysis report.

#### **9.1.3 Serious Adverse Events**

NOTE: The term serious is not synonymous with severity, which may be used to describe the intensity of an event experienced by the subject. An AE that does not meet any of the below criteria will be classified as non-serious.

A serious adverse event is any event that:

4. led to death,
5. led to serious deterioration in the health of the subject, that either resulted in:
  - 5.1. a life-threatening illness or injury, or
  - 5.2. a permanent impairment of a body structure or a body function, or
  - 5.3. in-patient or prolonged hospitalization, or
  - 5.4. medical or surgical intervention to prevent life-threatening illness or injury or permanent impairment to a body structure or a body function,
6. led to foetal distress, foetal death or a congenital abnormality or birth defect

Any adverse events or complications reported by the patient or observed by the physician that occur during or after treatment with the device will be recorded in the medical record or source document and on the dedicated Case Report Form. The investigator will determine if the AEs are device related or procedure related. This assessment shall include the onset date, resolution date, severity, seriousness, frequency, additional treatment required and outcome.

Each adverse event should be assessed according to the following criteria:

**Description: Surgical. Protocol LUM-SBU-VP-15-02, Ablation efficacy of contact side firing fiber in predefined settings for treating BPH**

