## 6 Patient Population

### 6.1 Source and Sample Size

Subjects shall be selected by the physician within his patient population. One (1) site will participate in this study and will treat twenty (20) subjects. Enrolled subjects that did not complete the full course of the study will be discarded from performance analysis if they have not returned for the 1 and/or 3 month follow-up visits.

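### For the symptom-type primary safety endpoints, the protocol does not state how absence is told from not asked, so the single-arm proportions may be underestimated

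*Combined protocol and SAP*

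**What the plan says.** Section 5.1.2.2 lists nine perioperative complications among the primary safety endpoints. One of them, "Erectile Dysfunction (International Score as compared to baseline"), names a score. Dysuria, haematuria, urge incontinence and stress incontinence are named without a definition, a question, an instrument or a time window.

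The rule for getting a complication into the data is in 9.1.3. It covers "Any adverse events or complications reported by the patient or observed by the physician" during or after treatment, and sends the event to the source record and a dedicated case report form. Table 1 (section 7.2) and Appendix I carry a row headed "Adverse Event Assessment", marked perioperatively, at discharge, at 1 month and at 3 months, but not at baseline. The content of that assessment is not described.

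Two further rules shape what is entered. Section 9.1.4.3 keeps a pre-existing condition out unless it has become substantially worse. Section 9.1.4.4 prefers a diagnosis to its component signs and symptoms when the diagnosis is reasonably certain.

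On analysis, 8.1 states: "Adverse events reported will be listed, documenting course, outcome, severity, and possible relationship to the treatment". It also says that "follow-up assessments will be summarized and descriptive analysis will be performed". Section 8.2 adds that "safety and adverse events report, durations and all endpoints will be analyzed following the completion of all study subjects follow-up period".

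**The concern.** A listing of reported events contains positives only. If no form asks about stress incontinence by name, a man with no entry may have been free of it, or nobody may have raised it. That status cannot be recovered at analysis. The items most exposed are symptoms that only the patient can perceive, and mild, transient ones in particular.

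The design raises the stakes: "This is a one arms, prospective, single center study". With no control group, incomplete capture cannot cancel between arms. It passes straight into the observed proportions, which are the primary safety result for these items.

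**Working it through.** **Inputs from the documents.** Sample size: "One (1) site will participate in this study and will treat twenty (20) subjects" (6.1). One arm (section 3). The documents give no expected complication rate, capture probability, precision target or missing-item rule, so there is no figure of the plan's own to reproduce.

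**Step 1: data source for each item in 5.1.2.2.**

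- Erectile dysfunction: scheduled at baseline and 3 months.
- Urinary retention: indirect cover from post-void residual ultrasound at baseline, 1 and 3 months.
- Infection: indirect cover from urine analysis at baseline and 3 months, with culture if applicable.
- Haematuria: partial cover from the same urine analysis, with nothing at discharge or 1 month.
- Re-catheterization and readmission: clinical acts that would normally leave a hospital record.
- Dysuria, urge incontinence, stress incontinence: no source beyond 9.1.3 and the undefined assessment row. The AUA and quality-of-life questionnaires are scheduled, but the protocol uses them for secondary endpoints (5.2) and does not tie them to these complications.

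The gap is therefore three items in full and haematuria in part.

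**Step 2: effect of the two recording rules.** Under 9.1.4.4, dysuria or haematuria attributed to a diagnosed infection could be entered only as infection, so the listing may not yield a count for the named endpoint. Under 9.1.4.3, a symptom counts only if new or substantially worse. These men enter with urinary symptoms (AUA score of at least 12, section 6.2.1), yet Table 1 schedules no named baseline check of dysuria, haematuria or incontinence. A new symptom could be set aside as old, and the form would not show it.

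**Step 3: scale of possible under-recording.** Let p be the true risk and q the probability that an affected man's event is recorded. Both are assumptions; q is varied from 0.5 to 1.

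Expected recorded count = 20 × p × q. Chance of recording none = (1 − p × q)^20.

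- p = 10%, q = 1: count 2.0; chance of none 0.90^20 = 12.2%.
- p = 10%, q = 0.7: count 1.4; 0.93^20 = 23.4%.
- p = 10%, q = 0.5: count 1.0; 0.95^20 = 35.8%.
- p = 20%, q = 1: count 4.0; 0.80^20 = 1.2%.
- p = 20%, q = 0.8: count 3.2; 0.84^20 = 3.1%.
- p = 20%, q = 0.5: count 2.0; 0.90^20 = 12.2%.

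**Step 4: what 0 of 20 would mean.** The exact two-sided 95% upper limit is 1 − 0.025^(1/20) = 16.8%. That limit applies to p × q, so the limit for p is 16.8% / q: about 21% at q = 0.8, 28% at q = 0.6 and 34% at q = 0.5.

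**Step 5: denominator.** Suppose 4 events are recorded and 4 men were not asked. Counting them as event-free gives 4/20 = 20%. Using those asked gives 4/16 = 25%. The extremes for all 20 men are 4/20 = 20% and 8/20 = 40%. Without a not-asked category, none of these can be told apart.

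**The case against.** The strongest reply is that the text does not prescribe spontaneous reporting. An answer to an investigator's question is also reported by the patient, and every subject has an assessment scheduled at four time points. A checklist would normally sit on a case report form; the forms are not in the supplied text, so its absence cannot be asserted. This stands, and it makes the point conditional. It does not close the gap: these are primary endpoints, and the protocol does not say that they are asked about.

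A reader might infer more than the documents support:

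- That all primary safety complications depend on volunteered reports. Blood loss and erectile dysfunction have scheduled measurements, intraoperative events are seen by the operator, and other items have indirect cover or leave records (Step 1).
- That the plan will only list events. Sections 8.1 and 8.2 also promise descriptive summaries and analysis of all endpoints. What is missing is the numerator, the denominator and the handling of items not asked.
- That no denominator can exist. Subjects assessed at each visit can be counted; subjects asked about a given item cannot, unless the form records it.
- That the proportions are biased low. No rate is stated, and the assumed range of q includes full capture, where there is no bias.

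It is also fair to say that the study is exploratory and imprecise: with perfect capture, 0 of 20 still leaves an upper limit of 16.8%. That limits what any safety proportion here can show. It is not a reason to leave the meaning of a blank open. Finally, prompting only after surgery could count pre-existing symptoms as complications. That objection is sound, and the change below therefore includes baseline.

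**Conclusion.** The point holds for dysuria, urge incontinence and stress incontinence, and in part for haematuria. For these items the protocol states a general capture rule, an assessment of undefined content and a listing. Unless the case report form prompts for each item, absence cannot be told from not asked, and the diagnosis and pre-existing-condition rules can remove further cases.

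The proportions may be underestimated; the documents do not give the amount. The figures above show scale only and rest on assumed p and q. At p = 10%, the chance of recording no case rises from 12% to 36% as q falls from 1 to 0.5. The change should be made, because the missing status cannot be reconstructed afterwards.

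**What to change.** In 9.1.3 and in the adverse event assessment row of Table 1 and Appendix I, require that dysuria, haematuria, urge incontinence and stress incontinence each be recorded by name as yes, no or not asked. Do this at baseline, perioperatively, at discharge, at 1 month and at 3 months; the row needs a baseline mark, which it now lacks. State that the item is recorded even when a diagnosis is also reported under 9.1.4.4. Other adverse events are recorded as now.

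In 8.1, report for each item the number of subjects with a new or worsened event over the number asked, with an exact 95% interval, beside the adverse event listing. If the case report form already prompts in this way, it is enough for the protocol to say so and for 8.1 to state the numerator and denominator.

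The cost is about one form page at visits already scheduled. The downside is that solicited rates may look less favourable than unprompted ones.
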